#### **Cell Counting**

The 56 laboratories will be asked to nominate primary screening staff to participate in the study. All slides in the study sets will be assessed for the presence of transformation zone indicators and each will have a formal cell count. The latter will be performed according to

protocols agreed with the Cytyc and TriPath Corporations to ensure corporate ownership of subsequent results. There is a tendency for Thin Prep® slides of low cellularity to show an uneven cell distribution with either a peripheral rim of enhanced cellularity and/or poorly cellular 'holes' which typically occur towards the centre of the deposit . SurePath™ preparations tend to be more homogeneous with an even cellular distribution throughout the deposit (Figure 2). Note also that the size of the cell deposits is different. These differences in cellular presentation between the two systems may need to be taken into account in determining the counting methodology and to ensure neither system is disadvantaged. As indicated in the original protocol a sub-study will be undertaken to establish robust methodologies for cell counting for both of the existing LBC systems. The Team acknowledges that there are flaws in the existing methodology recommended in the Bethesda Terminology System and is already working with the companies to ensure these are rectified. Once agreed, detailed standard operating procedures will be supplied to all participating laboratories.

It is not feasible for the material from the slide survey to be assessed for cellularity at a single centre. This would be a monumental task for any one laboratory even if distributed between a number of staff and could seriously impact on the routine service. The Study Team is of the view that this work should be distributed across all participating laboratories. In order to reduce bias due to inter-laboratory variability, a balanced design will be used with similar proportions of slides from each laboratory and of each cytological type being sent to each laboratory.

Cell count data will be entered on the pre-formatted disc and returned with the slide sets to the Study Centre.

#### **ARTISTIC / MCM Cases**

A further 1,200 cases previously documented as smear negative, HPV+ in the ARTISTIC/MCM trial will also be subject to cell counting according to protocols previously described. These cases represent true cytological false negatives and as such are a unique resource. Cell counts will determine whether there is a relationship between cellularity and false negative status. These will be compared with cell counts from both the negative and mildly dyskaryotic cases in part 1.

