# Design:

# **Laboratory Practice Survey**

This part of the study will be conducted in England through the national network of Regional Cervical Screening Quality Assurance Directors, and in Wales and Scotland through Cervical Screening Wales and the Scottish Cervical Screening Programme respectively. A total of 39 laboratories from the 9 English QA regions, 7 from Scotland and 10 from Wales to be recruited to ensure an approximately even representation of the two current LBC systems, giving a total of 56 laboratories (28 laboratories for each system). They will include a cross-section of low, intermediate and high workload laboratories and all will have implemented LBC for population based cervical screening for a minimum of 6 months post LBC training and accreditation. This will avoid recognised learning curve issues. The suggestion that the NHS LBC pilot sites and training centres should supply the bulk of the cases is impractical given the substantial imbalance in representation of the two LBC companies across those sites and would be likely to greatly extend study timescales.

All participating laboratories will be asked to nominate a Study Liaison Officer and a deputy. These persons will normally be senior BMS staff and will act as the contact point for all communication with the LBC Adequacy Study Centre. Each laboratory will initially be asked to complete a questionnaire which will cover the following points:

- Type of LBC system used
- Approximate date of completion of LBC training
- Date of full conversion to LBC
- Criteria used in laboratory for assessing adequacy including declared threshold, with copy of relevant laboratory Standard Operating Procedure (SOP)
- Copy of any other relevant SOPs e.g. cell counting methodology
- Current KC61 figures (DH return giving laboratory performance data) or equivalent data but to include only LBC cases (some labs may not have full 12 months LBC data)

Additional laboratories may be recruited to increase the total number undertaking slide assessments and to spread this workload more widely. The same requirements for study entry will apply as stated above, but these laboratories will not be asked to complete a questionnaire or to submit slides. It will be important to ensure an approximately even representation of the two LBC

[figure not shown]

Figure 1- Examples of normal and additional slide labels

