# **Slide Survey**

The 56 participating laboratories will be asked to submit 20 consecutive cervical screening LBC cases from each of the following report categories: inadequate, mildly dyskaryotic and high grade (moderate dyskaryosis and above). All high grade cases must be histologically confirmed. While histological confirmation of the mildly dyskaryotic cases is preferable it is acknowledged that this may not always be possible. It is important that as many cases as possible and certainly all high grade abnormalities are histologically proven to validate outcome. If outcome were determined by expert panel this could easily lead to a change in the original proffered diagnosis. This has serious and potentially negative implications for submitting laboratories and could lead to some declining participation.

Slides reported as borderline nuclear change will not be included in the study as this is a much less robust diagnostic category than higher grade abnormalities and its use is not consistently applied across laboratories.

50 consecutive negative cervical cytology LBC cases from the same time period will also be requested from each of these laboratories. They will be asked specifically not to pre-select good examples of individual diagnostic categories but to adhere strictly to number sequences. A total of 110 slides will thus be provided by each of the 56 laboratories resulting in a total of 6,160 slides in this arm of the study. Laboratories will have 3 months to gather and submit these slides.

Cases reported as inadequate because of the absence of transformation indicators following previous treatment of CIN, or the absence of endocervical cells in the case of previously treated CGIN will be specifically excluded from the study as the reason for inadequacy does not relate to specimen cellularity.

It is recognised that mucus and blood may block the filter pores in the Cytyc ThinPrep® LBC system. This problem should be addressed in routine work by the pre-treatment of the sample prior to a repeat preparation being made. The study will collect both the original preparation and any repeat preparations which have been made.

If additional preparations have been made, then all available slides should be submitted and included within the category of the issued cytological report, irrespective of the appearance of individual slides.

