Eight preparations will be made from each sample. Serial dilutions with approximate cellularities of 5-10k, 10-15k, 15-20k, 20-25k, 25-35k, 35-45k, 45-55k and 55+k will be made from half of the cases. The range of dilutions is skewed towards preparations of lower cellularity as these are expected to have higher false negative rates. The remaining cases will be mixed with known negative cases in varying proportion to establish sets of slides containing <25, 25-49, 50-99, 100-149, 150-199, 200-399, 400-799, 800-1600 and 1600+abnormal cells. In total 3,000 new slides will be prepared.

Each of the prepared slides will be assessed by two members of a four panel expert cytology group (to include [name]). Each slide will have a total cell count and a total abnormal cell count performed by the two panel members. Cases in which there is a variation of >10% between either of these counts will be assessed by at least three panel members on a multi-headed discussion microscope and a consensus decision reached.

The prepared slides will then be block randomised with 1,000 negative and 1,000 inadequate cases (total of 2,000) of similar cellularities in a ratio of 3:2 to minimise screener outcome bias.

Determination of "true" negative is always a problematic area in cervical cytology. In order to address this the Team proposes a modification to the existing protocol whereby 200 of the 1,000 negative slides will derive from confirmed HPV-ve cases. 100 of these HPV-ve slides will be acquired from archived material from the ARTISTIC/MCM trial. As the ARTISTIC/MCM trial used only Thin Prep® cases, these will be matched by newly acquired HPV-ve material from the SurePath™ system. It is estimated that 150 HPV tests will be required to obtain a cohort of HPV-ve, Cytology-ve cases.

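### The 1,200 smear-negative, HPV-positive slides are treated as proven false negatives without verification, and all are ThinPrep while the Part 1 comparators are about half SurePath

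*Protocol*

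**What the plan says.** The ARTISTIC / MCM Cases section in Part 1 of the Protocol adds cell counts on "A further 1,200 cases previously documented as smear negative, HPV+ in the ARTISTIC/MCM trial". It gives no further entry condition. It then assigns the group a status: "These cases represent true cytological false negatives and as such are a unique resource". The inference to be drawn is stated firmly: "Cell counts will determine whether there is a relationship between cellularity and false negative status". The comparators follow: "These will be compared with cell counts from both the negative and mildly dyskaryotic cases in part 1".

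The platform facts stand elsewhere. The Part 2 Design section explains the sourcing of HPV-negative slides with the words "As the ARTISTIC/MCM trial used only Thin Prep". The Laboratory Practice Survey section recruits evenly across the two systems, "giving a total of 56 laboratories (28 laboratories for each system". Under Slide Survey, each laboratory is asked for negatives ("50 consecutive negative cervical cytology LBC cases from the same time period will also be requested from each of these laboratories") and is to "submit 20 consecutive cervical screening LBC cases from each of the following report categories", one of which is mild dyskaryosis.

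The Part 1 Statistical Analysis section describes a logistic random effects model of the proportion of slides on either side of a threshold, with smear result and LBC system among the covariates. It does not mention the ARTISTIC/MCM slides. The Objectives section describes the same cohort neutrally, by its negative report and HPV-positive result.

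**The concern.** A cytological false negative needs an abnormality that was on the slide and was not reported. An HPV test shows infection. Some of the 1,200 women will have had no abnormal cells on the slide, and for them the negative report was right. A conclusion about cellularity and false-negative status would then attach to a group that the design does not identify.

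Separately, cellularity is the outcome, and the Part 2 Design section says that cell yield on the slide arises differently on the two systems: SurePath reflects the sample directly, whereas ThinPrep filters to a machine-set level. Comparing an all-ThinPrep group with a mixed group can show a difference that belongs to the platform.

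The two faults can act in opposite directions. Dilution can produce a null result against negatives that reads as reassurance about low cellularity, and platform mix can produce a difference where there is none.

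**Working it through.** **Plan's own figure.** The protocol gives no sample size, effect size or power for this comparison, so there is nothing to reproduce. The rates used below (1% and 2.5% below a threshold) are borrowed from the Part 1 Sample Size section as illustrations.

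**Step 1, the label.** Entry condition: negative smear plus HPV positive. Verification: the section describes no histology, follow-up or second reading, and Ethical considerations says that neither part reviews existing diagnoses. So nothing within the study separates missed abnormalities from correct negatives. The Part 1 negatives are not HPV-tested and may contain the same kind of case.

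**Step 2, platform counts.** Laboratories: 28 per system.

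| Group | ThinPrep | SurePath | Total |
|---|---|---|---|
| ARTISTIC/MCM | 1,200 | 0 | 1,200 |
| Part 1 negative | 28 × 50 = 1,400 | 1,400 | 2,800 |
| Part 1 mild | 28 × 20 = 560 | 560 | 1,120 |

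(The Part 1 Sample Size section writes 1,100 for mild; 56 × 20 = 1,120 is used here.)

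**Step 3, what an unadjusted comparison would carry.** With no true link, the ARTISTIC rate equals the ThinPrep rate T, and the pooled comparator rate is (T + S)/2, where S is the SurePath rate. The spurious difference is T − (T + S)/2 = (T − S)/2, half the platform difference. T and S are not given. Chance of a significant excess (two-sided 5% test, upper tail, 1,200 v 2,800 negatives):

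| T | S | Comparator | Ratio | Chance of excess |
|---|---|---|---|---|
| 1.0% | 1.0% | 1.0% | 1.0 | 2.5% |
| 1.5% | 0.5% | 1.0% | 1.5 | 29% |
| 2.0% | 0.5% | 1.25% | 1.6 | 44% |

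**Step 4, dilution against negatives.** Let f be the fraction of real misses, with 2.5% of these below threshold, and let the remainder behave like Part 1 negatives at 1%. The cohort rate is 0.025f + 0.01(1 − f), and the difference from negatives is 0.015f, that is, f times the undiluted difference. Power = Φ[(d − 1.96·SE₀)/SE₁], with SE₀ pooled and SE₁ unpooled, for 1,200 v 1,400 ThinPrep negatives. For f = 0.5: d = 0.0075, SE₀ = 0.00453, SE₁ = 0.00463, so z = −0.30 and power is 38%.

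| f | Cohort rate | Power |
|---|---|---|
| 100% | 2.5% | 83% |
| 50% | 1.75% | 38% |
| 20% | 1.3% | 11% |
| 10% | 1.15% | 6% |

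**Step 5, the mild comparison behaves differently.** There the difference is f(FN − mild) + (1 − f)(negative − mild), where FN is the rate in real misses. With FN = 2.5%, mild = 2.5% and negative = 1%, it is 0 at f = 100%, −0.75 points at f = 50% (1.75 − 2.5) and −1.2 points at f = 20% (1.3 − 2.5). Dilution here creates a difference instead of shrinking one.

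**Step 6, price of a same-platform comparison.** The standard error scales roughly with √(1/1,200 + 1/n). Against negatives: √[(1/1,200 + 1/1,400)/(1/1,200 + 1/2,800)] = √1.30 = 1.14. Against mild: √[(1/1,200 + 1/560)/(1/1,200 + 1/1,120)] = √1.52 = 1.23. In power terms, with the comparator at 1% and the cohort at 2.5%: 92% to 83% against negatives and 78% to 56% against mild.

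**The case against.** The best reply on platform is that this section lies within Part 1, whose model already lists LBC system as a covariate, and that the authors plainly knew ARTISTIC/MCM was ThinPrep only, since they match its HPV-negative slides with SurePath material in Part 2. Handling a secondary comparison can also be left to the analysis plan. This stands in part. A reader might infer that a crude pooled comparison is planned and that half the platform difference is bound to enter; the protocol does not say so, and Step 3 holds only if the analysis is unadjusted. But the covariate is never tied to the ARTISTIC slides, and the comparators are named without any platform limit.

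A reader might also take the different deposit sizes as a bias in themselves. They are not: deposit area is a term in the total-count formula under Slide Survey, and a sub-study sets the counting method for each system.

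On the label, it can be said that histology is required only for high-grade cases and merely preferred for mild ones, and that Part 2 itself uses HPV-negative status to firm up true negatives. So the protocol does not break a uniform histology rule. But an HPV-negative result making a negative report more secure does not mean that an HPV-positive one proves it wrong. What the source trial recorded on follow-up cannot be seen here.

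Finally, the stated inference is a relationship, not causation, and no sample size rests on it. Both points are correct and limit the consequence.

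**Conclusion.** The point holds on both counts. The label claims more than the entry condition can support, no analysis can repair that, and adjusting for platform does not touch it. The comparison as written also sets an all-ThinPrep group against comparators that are about half SurePath, with no stated restriction or adjustment.

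The size is conditional. Shrinkage of the contrast to f of its value applies only against negatives, and only if the slides without a missed abnormality resemble Part 1 negatives; f is unknown. A reader might extend this to the mild comparison, but Step 5 shows that it does not carry over. The platform figures rest on assumed rates and an unadjusted analysis.

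Nor do the documents support reading this as a flaw in the adequacy threshold: that is to come from the Part 2 pick-up model, which does not draw on this comparison as written.

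**What to change.** 1. Call the group smear negative, HPV positive throughout, as Objectives already does in substance, and limit the conclusion to cellularity in that group. Reserve the term false negative for any cases with a histologically confirmed abnormality in existing source-trial records, if such records are available.
2. State that the comparison is made within ThinPrep (about 1,400 negative and 560 mild slides). Alternatively, state that the ARTISTIC/MCM slides enter the Part 1 model as an added level of smear result, with LBC system as a covariate.

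Neither step needs new slides. Restriction gives up half the comparators and some precision, mainly against mild cases (Step 6). The covariate route keeps all slides but relies on the platform effect being alike across smear results.

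The 100 HPV-negative ARTISTIC/MCM slides in Part 2 should not be used as a same-platform control. The Part 2 negatives are chosen to be of similar cellularity to the prepared slides, so their cellularity is set by selection.

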# Sample Size

Declared inadequate slides will be used to determine the distribution of cellularity in such slides. With a sample of 1,120 a proportion of say 5% falling above the specified threshold can be estimated with a 95% distance from the percentage to the 95% c.i. of 1.3%. Declared negative slides will be used to estimate the proportion falling below the specified threshold. With 2,800 slides a proportion of 1% falling below the required threshold can be estimated with distance from the percentage to the 95% c.i. of 0.4%. We hypothesise that the greatest proportion of slides with low cellularity will be seen in mildly dyskaryotic slides and lowest proportion in negative slides, with high-grade dyskaryotic slides between the two. With 2,800 negative slides, 1,120 high grade and 1,100 mildly dyskaryotic slides, a chi-squared test of trend will have a power of 87% to detect a difference between 1% of negative slides falling below a threshold increasing to 2.5% in the mildly dyskaryotic cases and a power of 74% to detect an trend increasing from 1% to 2%.

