# **Statistical Analysis**

Statistical analysis would be used estimate the proportion of slides falling above or below the specified threshold. Covariates for smear result, "LBC system" and relevant data from the survey of practice would be included as covariates in logistic random effects model of the proportion falling either side of the specified threshold. This analysis would be carried out using each laboratory's current threshold and that derived in part 2 of the study.

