# **Sample Size**

To have 80% power to compare a 95% pick-up rate in more cellular slides with an 80% pick-up rate in less cellular slides would require 90 slides in each bands of cellularity. Power will be increased by each slide being read by three reviewers. This can be estimated by applying a cluster sampling correction. If the agreement between reviews has a kappa coefficient of 0.75, power will increase to 87%. In total 1,440 slides would be required for each system (720 high grade / 720 mild moderate). A further 960 cases will be included of similar cellularity. These estimates ignore the matching of slides across bands. If this matching of slides can be incorporated in the statistical analysis, power will increase slightly.

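### Part 1's stated precision ignores sampling by laboratory, and its two trend-test powers do not follow from one common set of assumptions

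*Protocol*

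**What the plan says.** The Sample Size section for Part 1 makes two precision statements.

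- Inadequate slides: "With a sample of 1,120 a proportion of say 5% falling above the specified threshold can be estimated". The margin it claims is 1.3 percentage points either side.
- Negative slides: "With 2,800 slides a proportion of 1% falling below the required threshold can be estimated". Here the claimed margin is 0.4 percentage points either side.

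The same section expects low cellularity to be least frequent in negative slides, more frequent in high-grade slides and most frequent in mildly dyskaryotic slides. For a chi-squared trend test on 2,800 negative, 1,120 high-grade and 1,100 mild slides it claims 87% power when the proportion rises from 1% to 2.5%, and "a power of 74% to detect an trend increasing from 1% to 2" (per cent). It gives no alpha, sidedness, scores or high-grade rate.

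The sampling is set out under Slide Survey: "The 56 participating laboratories will be asked to submit 20 consecutive cervical screening LBC cases from each of the following report categories", namely inadequate, mild and high grade, plus 50 consecutive negatives from each laboratory. The Part 1 Statistical Analysis section plans a "logistic random effects model of the proportion falling either side of the specified threshold".

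**The concern.** Slides from one laboratory share smear takers, local procedures and a local adequacy rule. The Background section describes declared thresholds of 5,000 and 15,000 cells and considerable subjectivity in applying them. The proportion of slides on the wrong side of a threshold may therefore vary between laboratories, and the planned random effects model allows for such variation. The precision statements do not.

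These proportions are what Part 1 will use to say how closely practice matches declared criteria. If the planning figures are too narrow, readers will expect more certainty than the design gives.

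The two powers rest on the same test and the same group sizes, so one set of assumptions should yield both. If it does not, a reader cannot tell how well the smaller trend is powered.

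**Working it through.** **1. Reproducing the half-widths.** Inputs are n and p from the Part 1 Sample Size section. The formula is 1.96 × √(p(1−p)/n).

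- Inadequate: 1.96 × √(0.05 × 0.95/1,120) = 1.96 × 0.00651 = 1.28 points (stated 1.3).
- Negative: 1.96 × √(0.01 × 0.99/2,800) = 1.96 × 0.00188 = 0.37 points (stated 0.4).

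The arithmetic is right for independent slides; the design effect is exactly 1.

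**2. Allowing for laboratory.** The design effect is 1 + (m−1) × ICC, with m = 20 for inadequate and m = 50 for negative slides. The half-width is multiplied by its square root. The ICC values are assumptions, since the protocol gives none.

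| ICC (assumed) | Inadequate: design effect | Half-width (points) | Negative: design effect | Half-width (points) |
|---|---|---|---|---|
| 0.005 | 1.095 | 1.34 | 1.245 | 0.41 |
| 0.01 | 1.19 | 1.39 | 1.49 | 0.45 |
| 0.02 | 1.38 | 1.50 | 1.98 | 0.52 |
| 0.05 | 1.95 | 1.78 | 3.45 | 0.68 |
| 0.10 | 2.90 | 2.17 | 5.90 | 0.90 |

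**3. Trend power.** Scores s are 0 (negative), 1 (high grade) and 2 (mild), with n = 2,800, 1,120 and 1,100. The mean score is (1,120 + 2,200)/5,020 = 0.661. Define

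- U = Σn(s−s̄)p
- V0 = p̄(1−p̄)Σn(s−s̄)²
- V1 = Σn(s−s̄)²p(1−p)
- power = Φ[(U − z√V0)/√V1]

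Two-sided 5% (z = 1.96), high-grade rate at the midpoint:

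- 1%, 1.75%, 2.5%: U = 24.93, V0 = 48.99, V1 = 62.38. (24.93 − 1.96 × 7.00)/7.90 = 1.42, so power is 92.2% (stated 87%).
- 1%, 1.5%, 2%: U = 16.62, V0 = 43.65, V1 = 52.66. (16.62 − 1.96 × 6.61)/7.26 = 0.51, so power is 69.4% (stated 74%).

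Simulation gave 93% and 69%. One-sided 5% (z = 1.645) gives 95.5% and 78.6%.

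**4. Can another high-grade rate reconcile them?** Keeping the two-sided 5% test and moving the high-grade rate over its whole permitted range:

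- First scenario: power runs from 87.8% (high grade 1.0%, equal to negative) to 95.3% (2.5%, equal to mild). The stated 87% lies just below the floor.
- Second scenario: power runs from 62.6% (1.0%) to 75.5% (2.0%). The stated 74% needs about 1.9%.

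The high-grade rate would have to rise from about 1.0% to about 1.9% while the mild rate falls from 2.5% to 2%.

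**5. Other conventions.** A search over 77,490 combinations of alpha, sidedness, variance form, continuity correction, middle score, high-grade position and mild-group size found none within 2 points of both stated values. With the high-grade score between the other two, the closest two-sided 5% setting gave 91.5% and 69.5%, and the closest one-sided 5% setting 90.4% and 70.7%. The closest of all used a one-sided 10% test with the high-grade score almost equal to the negative score: 89.2% and 72.1%.

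**6. Group size.** 56 × 20 = 1,120, not 1,100 mild slides. With 1,120 the two-sided midpoint powers are 92.4% and 69.7%. The discrepancy is real but does not explain the mismatch.

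**The case against.** The half-widths contain no arithmetic error, and the planned random effects model can deal with laboratory at analysis. How intervals are computed could also be left to an analysis plan that is not shown. This stands as a limit on the point: what is at issue is the precision the protocol states, not a fault in the analysis model. With a small ICC the stated figures are nearly right (1.34 and 0.41 at 0.005).

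Four stronger readings are tempting and not supported.

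- *That Part 2 corrects for laboratory clustering and Part 1 forgot to.* Part 2 does say "This can be estimated by applying a cluster sampling correction", but that concerns three readings of the same slide, not laboratory of origin.
- *That Part 1 sets out to show that laboratories differ, so the ICC must be large.* Its stated purpose is to compare declared with operating thresholds. One of the two planned analyses uses each laboratory's own threshold, so differing thresholds are already built into that outcome. The size of the ICC is open.
- *That 92% and 69% are the correct powers.* They hold for one reasonable set of assumptions. The hypothesis is directional, and a one-sided test gives about 96% and 79%, which would make both stated values conservative.
- *That clustering undermines the trend test as well.* Each laboratory contributes to all three categories, so a shared laboratory effect largely cancels in that comparison.

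**Conclusion.** The point holds in two limited parts.

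First, the half-widths of 1.3 and 0.4 points are valid only for independent slides. For any positive between-laboratory ICC they are too narrow. The direction is certain and the size is not: from almost nothing at ICC 0.005 to 2.17 and 0.90 points at 0.10. Negative slides are the more exposed because each laboratory supplies 50 of them.

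Second, 87% and 74% do not come from any single rule that was tried. At two-sided 5% with even spacing, the first is about 5 points too low and the second about 5 points too high. Matching both two-sided requires unlinked high-grade rates of about 1.0% and 1.9%. Because the section omits alpha, sidedness and the high-grade rate, the supported conclusion is that the pair is not reproducible, not that particular replacement values are right.

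Neither part shows that the number of slides is inadequate.

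**What to change.** In the Part 1 Sample Size section:

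- Restate both half-widths with the design effect 1 + (m−1) × ICC, m = 20 and 50, over a stated ICC range that includes the low end.
- Say that Part 1 proportions will be reported with intervals that allow for laboratory of origin.
- Recompute both trend powers under one stated alpha, sidedness and rule for the high-grade rate. If two-sided 5% with even spacing is chosen, the results are about 92% and 69% (69.7% with the corrected group size).
- Replace 1,100 mild slides with 1,120.

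The cost is wording; no slide numbers change. The stated precision becomes less favourable, as does the power for the smaller trend if the test is two-sided.
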